6.2. Rationale

There is a need to understand the CAB and/or RPV LA containing regimens utilization in a real-world clinical setting. Adherence to scheduled dosing visits to help maintain viral suppression and reduce the risk of viral rebound and potential development of resistance with missed doses is critical for long term maintenance of viral suppression. Impact of non-adherence on virologic failure and emergence of resistance need to be assessed in a real world clinical setting among a more heterogeneous population than often represented in clinical trials.

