Descriptive analyses will compare those with and without virologic failure to assess any differences in baseline characteristics of the two groups. Detailed analysis of additional risk factors will be limited to persons with 6, 12 or 24 months of follow-up. Multivariable logistic regression models will investigate the factors associated with virologic failure at 6 months, 12 months and 24 months after CAB+RPV LA initiation. Potential explanatory variables are listed above. We will also investigate the impact of missed doses and use of oral bridging therapy by using the data collected via the CRF. Multivariate analyses will be performed when > 30 persons on CAB+RPV LA have virologic failure and analyses will be limited to persons with > 6-, 12- or 24-months follow-up. The model building strategy will follow EuroSIDA protocol and include variables significant in univariate analyses as well as *a priori* pre-specified variables of interest. Primary analysis for clinical effectiveness will include individuals on CAB+RPV LA, with VL of <50/copies/mL at regimen initiation. In addition, all the analyses will be conducted separately for individuals on CAB+RPV LA with VL of ≥50 copies/mL at regimen initiation.

Our primary analyses of virologic outcomes will censor follow-up at discontinuation of CAB+RPV LA, last visit or death, whichever occurs first, an on-treatment approach to analysis. Sensitivity analyses will use an intent to treat approach and virologic outcomes will be assessed regardless of regimen discontinuation.

We will perform additional sensitivity analysis limited to those who start CAB+RPV LA with resistance data available, to confirm no present or past evidence of viral resistance to, and no prior virological failure with agents of the NNRTI and INSTI class.

AIM 4. Monitor for resistance and next treatment response among individuals who switched off CAB+RPV LA regimen

Monitoring for resistance

Since this is a non-interventional study aiming to capture individual care in real world setting, the study will not mandate resistance testing following discontinuation of the regimen of interest. Health care providers following the local treatment guidelines decide

what laboratory and resistance tests are to be conducted. Data thus generated will be captured and analyzed by the study team.

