Descriptive statistics will describe and compare the ARV regimen individuals are switched to after discontinuation of CAB+RPV LA regimen. As resistance testing will not be common, we will describe the characteristics of those with and without resistance testing at virologic failure and again at virologic failure during the 12, 24, 36 and 48 months after switching regimens and use logistic regression to identify factors associated with resistance testing. Where more than 1 resistance test is available during the 12, 24, 36 and 48 months after stopping CAB+RPV LA regimen, cumulative resistance data will be collected and reported.

Study will monitor for resistance at virologic failure and again at virologic failure during the 12, 24, 36 and 48 months following the switch, where resistance data are available. Resistance patterns in those with resistance testing will be summarized. Depending on the number of resistance tests performed and amount of resistance detected, logistic regression will be used to identify factors associated with resistance to CAB+RPV LA. Potential explanatory variables are listed above including missed and delayed doses and use of bridging therapy.

Next treatment response

The study will describe virologic success at 12, 24, 36 and 48 months after discontinuation of CAB+RPV LA regimen, using virologic failure definition as described above. Given that this study involves persons in routine clinical care, and who may not attend clinic appointments every 12 months, a window of 12 weeks around the date in question will be used for virologic testing data. Thus, the proportion with virologic success at 12, 24, 36 and 48 months \pm 6 weeks will be used; and if none is available, the first measurement after 6 or 12 months will be used.

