(After completion of date of second injection, a new section will open for third injection with target date two month/3 months [for monthly and 2 monthly schedules, respectively] after the first injection. As long as the patient receives injections as scheduled, the target date for the next injection is determined by the start date ± 1 month/2 months ± 7 days for each injection depending on schedule)

(All injections until 24 months+ six weeks after initiation of LAI will be collected)

If no to question whether planned injection has been given, following question will appear:

	Has the patient started bridging therapy?								
		YES			NO				
If yes, new question will show:									
Reason for starting bridging therapy (LAI drugs out of stock,									
1 '	•	to come for the	•						
injection site	adverse effe	t, other + text fie	ld)						
Start date:				Has th	e patient	later res	started long-actin	g antiretroviral therapy?	
Stop date:									
			estion will show:						
Has the patie	nt restarted	ong-acting antire	troviral therapy?		YE	ES		NO	
	YES		NO						
Which long-ad		ive been given?	Reasons for	Which long-acti				Reasons for discontinuation	
long acting	2) long	3) long	discontinuation	long acting	2) long	•	3) long acting		
cabotegravir	acting	acting	(drop down	cabotegravir+	cabote	-	rilpivirine	*If death – please complete	
+ long	cabotegrav		menu with all	long acting	without		without	CoDe form	
acting	without	without	reasons in table	rilpivirine	rilpivirir	ne	cabotegravir	*If liver, other or unknown	
rilpivirine	rilpivirine	cabotegravir	3 in the					causes – please complete	
	• •	/ 600/900 mg	protocol)	Dosage: 400/60		B)/600/	900 mg (RPV)	hepatotoxicity form	
(RPV) (drop de	•			(drop down menu)			1		
Date of injecti			*If death —	Date of injection:			_		
	tended sche		please		ntended			1	
Monthly	Eve	y 2 Month	complete CoDe	Monthly		Every 2	Month		
			form						
			*If liver, other						
			or unknown						
			causes – please complete						
			hepatotoxicity						
			form						

(All those reported CAB + RPV discontinuations due to virological failure (reason 1, 1.1, 1.2) will prompt collection of resistance test results. A reminder will be sent after 1 and 2 years of follow up after failure. In addition to these specific reasons prompting collection of HIV resistance testing data, we will also perform checks for viral load>limit of detection to identify people with viral failure)

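### The Aim 4 resistance model conditions on failure and testing, so by itself it cannot show whether missed doses lead to emergent resistance, and no per-starter resistance analysis is planned beside it

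*Protocol*

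**What the plan says.** Section 6.2 of the protocol sets the question: "Impact of non-adherence on virologic failure and emergence of resistance need to be assessed in a real world clinical setting".

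Section 8.6, Aim 4, is where resistance is analysed. Testing is left to routine care: "the study will not mandate resistance testing following discontinuation of the regimen of interest". Resistance is looked for at failure: "Study will monitor for resistance at virologic failure and again at virologic failure during the 12, 24, 36 and 48 months following the switch", where data exist. Then comes "Resistance patterns in those with resistance testing will be summarized". The next sentence opens with a condition, "Depending on the number of resistance tests performed and amount of resistance detected", and continues "logistic regression will be used to identify factors associated with resistance to CAB+RPV LA". The predictors follow: "Potential explanatory variables are listed above including missed and delayed doses and use of bridging therapy".

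Annex 1 shows how the outcome reaches the database: CAB+RPV "discontinuations due to virological failure (reason 1, 1.1, 1.2) will prompt collection of resistance test results". Viral loads above the limit of detection are also checked to find further failures. The follow-up resistance form is headed as applying after virological failure and asks about tests done after CAB+RPV LA was stopped.

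Three other parts of the protocol bear on this. Section 8.6, Aim 3, examines missed doses and bridging in the virologic failure analysis. Aim 4 also describes and models who gets a resistance test. Section 8.8 warns that testing may be targeted and that results may not carry over to the whole study population.

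**The concern.** To ask whether non-adherence leads to resistance is to compare non-adherent with adherent users of the regimen, most of whom are not expected to fail. The Aim 4 model can use only people whose resistance status is known. Those are people with a test, mostly after failure or discontinuation.

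Missed doses help to create that group. Section 6.2 itself ties them to viral rebound, and section 8.3.2 defines discontinuation by a missed injection without bridging. Within the group, a person who missed doses is compared with other people who failed and were tested, not with people who stayed suppressed. The coefficient for missed doses answers a narrower question: given failure and a test, who has resistance?

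At stake is how the coefficient is read. In a post-authorisation study that also evaluates risk minimisation for adherence (Objective 5), a null or inverse coefficient for missed doses could be taken as reassurance when missed doses raise the number of people with resistance.

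**Working it through.** **1. Plan's own figures.** The protocol gives no event count, effect size or numeric threshold for the resistance model, so there is nothing on this point to reproduce. The illustration is anchored on the Table 4 row N = 1000, P = 0.02, which means 20 failures. Exact Clopper-Pearson limits for 20/1000 are 0.0123 to 0.0307, which agrees with the stated 0.012 to 0.031.

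**2. Assumptions, none from the protocol.** 20% of starters are non-adherent (800 adherent, 200 non-adherent). Failure risks, adherent/non-adherent, are 1.5%/4% (12 + 8 = 20 failures) or 1%/6% (8 + 12 = 20 failures). Resistance given failure is varied in both directions. Table 4 gives only pooled rates, so any split by adherence is an assumption.

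**3. Formulas.** Let f be the failure risk, r the probability of resistance given failure, and subscripts a and n adherent and non-adherent.
- Risk of failure with resistance per starter = f × r.
- Risk ratio among all starters = (f_n / f_a) × (r_n / r_a).
- Odds ratio among all starters = odds(f_n r_n) / odds(f_a r_a).
- Odds ratio among tested failures = odds(r_n) / odds(r_a).

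If a fraction t of failures is tested and t depends on adherence only, tested failures split as f·t·r resistant and f·t·(1 − r) not. Then t cancels, and testing 70% vs 30% gives the same odds ratio as 50% vs 50%. The main cause is restriction to failures. Testing distorts further only if it depends on adherence and resistance jointly.

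**4. Results.**

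| f_a / f_n | r_a / r_n | Resistance per starter, a / n | Risk ratio, all | Odds ratio, all | Odds ratio, tested failures |
|---|---|---|---|---|---|
| 1.5% / 4% | 0.3 / 0.6 | 0.45% / 2.4% | 5.33 | 5.44 | 3.5 |
| 1.5% / 4% | 0.5 / 0.5 | 0.75% / 2.0% | 2.67 | 2.70 | 1.0 |
| 1.5% / 4% | 0.6 / 0.4 | 0.9% / 1.6% | 1.78 | 1.79 | 0.44 |
| 1.5% / 4% | 0.7 / 0.4 | 1.05% / 1.6% | 1.52 | 1.53 | 0.29 |
| 1% / 6% | 0.3 / 0.6 | 0.3% / 3.6% | 12.0 | 12.41 | 3.5 |
| 1% / 6% | 0.5 / 0.5 | 0.5% / 3.0% | 6.0 | 6.15 | 1.0 |
| 1% / 6% | 0.6 / 0.4 | 0.6% / 2.4% | 4.0 | 4.07 | 0.44 |
| 1% / 6% | 0.7 / 0.4 | 0.7% / 2.4% | 3.43 | 3.49 | 0.29 |

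Higher assumed failure risks give the same pattern (odds ratio among all starters, then among tested failures). For 2%/10%: 5.26 and 1.0 (r 0.6/0.6), 3.43 and 0.44 (0.6/0.4), 4.13 and 0.67 (0.5/0.4). For 5%/20%: 2.81 and 0.44 (0.6/0.4).

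On the risk-ratio scale, the failures-only comparison always lacks the factor f_n / f_a. A true reversal needs r_n / r_a below 1 but above f_a / f_n, which is 1.5/4 = 0.375 in the first set; 0.4/0.6 = 0.67 and 0.4/0.7 = 0.57 both qualify. Where r_n exceeds r_a the direction is kept. In the cases run, the odds ratio is also weakened, but that need not hold if resistance among failures is very common.

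**5. What untested failures do.** Take 1.5%/4%, r = 0.5 in both groups, and half of failures tested (assumed). Adherent: 12 failures, 6 tested, 3 resistant, 6 unknown. Non-adherent: 8 failures, 4 tested, 2 resistant, 4 unknown.
- Unknowns all without resistance: 3/800 = 0.375% vs 2/200 = 1.0%.
- Unknowns all with resistance: 9/800 = 1.125% vs 6/200 = 3.0%.

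Both give a ratio of 2.67. Opposite extremes in the two groups give 1.0/1.125 = 0.89 to 3.0/0.375 = 8.0. Only five resistance events are observed.

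**The case against.** **The denominator is not stated.** A reader might infer that the protocol declares tested failures to be the comparator. It does not: the regression sentence names no population, and the analysis set could be fixed in an SAP that is not at hand. The inference is strong all the same, because the outcome is unknown without a test. Even the broadest Aim 4 population, all discontinuers, leaves out adherent people who stay on treatment.

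**Objective 4 asks for less.** It covers people who discontinued and were tested, and the Annex 2 checklist disclaims hypotheses and comparators. A model within tested people is valid for that objective. This stands: the model is not wrong in itself. It falls short only of the question in section 6.2, which no other analysis takes up.

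**Aim 3 covers missed doses.** A reader might infer that the plan ignores how missed doses act through failure. It does not, and a report showing both aims would lessen the risk of misreading. But Aim 3 stops at failure, its multivariable model needs more than 30 failures (the anchor row gives 20), and its primary analysis censors at discontinuation, which a missed unbridged injection triggers. An intent-to-treat sensitivity analysis is planned, yet nothing joins it to resistance.

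**Selection is disclosed.** Section 8.8 and the tested-versus-untested comparison address representativeness. They do warn against a whole-cohort reading, but they do not address what missed doses are compared with.

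**The inputs are chosen.** This also stands. The protocol gives no failure risk or resistance rate by adherence, and if resistance is more frequent in non-adherent failures the direction is right.

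**Conclusion.** The point holds as a limit on what the Aim 4 model can show. With an outcome known only in tested people, it estimates resistance given failure and testing, and cannot by itself tell whether non-adherence leads to emergent resistance.

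The size depends on assumed inputs. With failure risks of 1.5% and 4%, odds ratios among all starters of 2.70, 1.79 and 5.44 correspond to 1.0, 0.44 and 3.5 among tested failures. The effect vanishes if resistance given failure is equal by adherence. It can reverse if resistance given failure is lower in non-adherent people. If it is higher, the direction is kept, with a weaker effect in the case run.

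A reader might go further and conclude that the study will report missed doses as harmless or protective. The documents do not support that: they give no rates by adherence, the model is conditional on numbers and may never be fitted, and Aim 3 would show any excess of failures among non-adherent people. What is missing is an analysis that puts the two parts together, and a label that stops the tested-only result being read as the impact of non-adherence.

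**What to change.** - **Add a per-starter summary.** Report the proportion of all CAB+RPV LA starters with virologic failure and detected CAB or RPV resistance over a fixed horizon. Annex 1 collects injections to 24 months plus six weeks, so 24 months is feasible.
- **Classify exposure before the outcome.** Show it by adherence and bridging status taken from injections due before failure, or as time-updated exposure, because adherence accrues after baseline.
- **Count failures after a missed-dose discontinuation.** Censoring there would remove the cases the question is about.
- **Give bounds.** Treat untested failures as all without and then all with resistance. Do not simply count them as non-resistant.
- **Fit a regression only if events allow.** Otherwise leave it as a table.
- **Report and label.** Place it beside the Aim 3 failure result. Name the population of the tested-only model and label it as conditional on failure and testing, not as the impact of non-adherence.

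The cost is one table, some exposure coding and a few sentences. Starters, injection dates, viral loads and test reports are already to be collected. The downside is precision: bounds will be wide and events few, as step 5 of the working shows. When many failures are untested, the upper bound comes close to the Aim 3 failure comparison.

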2. Clinical effectiveness: Primary analysis for clinical effectiveness will include only those initiating the regimen per label i.e. initiating CAB+RPV LA with VL<50 copies/mL at regimen initiation. The following VL measures will be used for effectiveness assessment:

- 1. Proportion of individuals, virologically suppressed/undetectable (<50 copies/mL) at 6, 12 and 24 months following initiation of CAB+RPV LA regimen
- 2. Proportion of individuals with VL <200 copies/mL at 6, 12 and 24 months following initiation of CAB+RPV LA regimen
- 3. Proportion of individuals with confirmed virologic failure (CVF) during the first 6 months, and at 6, 12 and 24 months following initiation of CAB+RPV LA regimen defined as:
 - Two consecutive HIV RNA VL levels ≥200 copies/mL or
 - One HIV RNA VL level ≥200 copies/mL and regimen discontinuation within 4 months of VL ≥200 copies/mL

3. Resistance Testing:

Since this is a non-interventional study aiming to capture individual care in real world setting, the study will not mandate resistance testing following discontinuation of CAB+RPV LA regimen. Health care providers following the local treatment guidelines decide what laboratory and resistance tests are to be conducted. Data thus generated, including available HIV-1 subtypes, will be captured and analyzed by the study team.

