Non-adherence to dosing schedule will be assessed by estimating the number of individuals that missed one or more consecutive injections without taking daily oral bridging therapy or any other oral ARV regimen while not on CAB+RPV LA regimen and median number of injections missed during a 12-month period. We will also estimate the number who received the injections seven or more days later than their scheduled injection visit and median duration of delayed injections in persons using bridging therapy. In addition, the number of individuals who missed one or more consecutive injections without taking daily oral bridging therapy or those who received the injections seven or more days later than their scheduled injection visit will be assessed and patient characteristics for those individuals that are non-adherent will be described.

Logistic regression will be used to identify factors associated with not starting CAB+RPV LA in those that start lead in, to compare those missing injections where bridging treatment is used, non-adherence and to identify factors associated with discontinuation of CAB+RPV LA (when there are more than 30 endpoints). Potential explanatory variables are listed above. The model building strategy will follow EuroSIDA protocol and include variables significant in univariate analyses as well as *a priori* pre-specified variables of interest.

AIM 3. Assess the clinical effectiveness (i.e. proportion individuals experiencing virologic failure and proportion with undetectable VL) among PLWH who initiate CAB+RPV LA regimen

The study will estimate the proportion with virologic failure during the first six months and at six, twelve and twenty four months after the start of the treatment with injectable regimen. Given that this study involves persons in routine clinical care, and who may not attend clinic appointments at 6, 12 or 24 months, a window of 12 weeks around the date in question will be used for virologic failure. Thus, the proportion with virologic failure during first six months, at 6, 12 or 24 months \pm 6 weeks will be used; and if none is available, the first measurement during first six months, after 6, 12 or 24 months (and at most 6 weeks after the measurement).

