Descriptive analyses will compare those with and without virologic success at 12, 24, 36 and 48 months after stopping the CAB+RPV LA regimen, as well as the next regimen started and time to start the next regimen following discontinuation of the regimen. If numbers allow for further analyses, multivariable logistic regression models will investigate the factors associated with virologic success at 12, 24, 36 and 48 months after switching off CAB+RPV LA regimen. Potential explanatory variables are listed above. Multivariate analyses will be performed when > 30 persons in the relevant treatment group have virologic success and analyses will be limited to persons with > 12 months follow-up. The model building strategy will follow EuroSIDA protocol and include variables significant in univariate analyses as well as *a priori* pre-specified variables of interest.

AIM 5. Evaluate the effectiveness of routine risk minimisation measures for regimen adherence, discontinuation due to incorrect route of administration and off-label use of CAB+RPV LA regimen

The purpose of this aim is to monitor to see if label guidance is adhered to, off label usage, adherence and discontinuation due to incorrect route of administration. This analysis on effectiveness of routine risk minimisation measures will be stratified for each region in the Eurosida cohort.

Analysis of off-label users – regimen combinations other than CAB+RPV LA (b -g in objective 1)

Descriptive Analysis:

As noted in Aim 1 above, analysis will be performed on the off-label users of CAB and/or RPV LA containing regimens. They will be characterized using demographics, clinical, immunologic and virologic characteristics at baseline (i.e. at initiation of regimen) stratified by different regimens noted in groups b-g above.

Adherence and Discontinuation:

Non-adherence to the dosing schedule and discontinuation due to incorrect route of administration will be assessed as described under Aim 2.

Clinical Outcomes:

Analysis will be conducted for the off-label users of CAB and/or RPV LA containing regimens separately to assess clinical outcome similar to description under Aim 3 above.

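### Aim 4 next-treatment response: the fallback for a missing viral load is not tied to the 12- to 48-month targets, success has no definition of its own, and the model threshold counts successes rather than the rarer outcome

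*Protocol*

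**What the plan says.** All references are to the Protocol.

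- **Outcome and times (8.6, AIM 4, Next treatment response).** The outcome is given as "virologic success at 12, 24, 36 and 48 months after discontinuation of CAB+RPV LA regimen, using virologic failure definition as described above".
- **Window.** Because routine-care patients may not attend on schedule, "a window of 12 weeks around the date in question will be used for virologic testing data", that is ±6 weeks.
- **Fallback.** "if none is available, the first measurement after 6 or 12 months will be used".
- **Failure definition that is invoked (8.3.2, Clinical effectiveness).** Confirmed virologic failure (CVF) has two arms. The first reads "Two consecutive HIV RNA VL levels ≥200 copies/mL or"; the second is one VL of at least 200 copies/mL with regimen discontinuation within 4 months of it. The same list holds two single-VL measures, below 50 and below 200 copies/mL, but only at 6, 12 and 24 months from initiation.
- **Model rule (8.6, AIM 4).** "Multivariate analyses will be performed when > 30 persons in the relevant treatment group have virologic success". The sentence goes on to require more than 12 months of follow-up. A preceding proviso makes further analysis depend on the numbers available, without giving one.
- **Parallel rules (8.6, AIM 3).** The fallback there is "the first measurement during first six months, after 6, 12 or 24 months (and at most 6 weeks after the measurement"). The model starts when more than 30 persons have virologic *failure*, and follow-up is matched to the 6-, 12- or 24-month point. The off-label analysis under AIM 5 also counts failures.

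**The concern.** Objective 4 asks how people fare for up to 48 months after stopping the regimen, and a supplemental report is timed to that follow-up (Section 5). Three rules decide what that report will show: which VL represents each time point, what counts as success, and when a model is fitted.

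As written, the first rule does not fit its own time points, the second borrows a definition made for a different situation, and the third guards the wrong side of a binary outcome. Two analysts following the text could report different proportions from the same data. A model could also be fitted with very few failures, or none.

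**Working it through.** The plan states no sample size or precision for Aim 4, so there is no figure to reproduce. The window agrees with itself: 2 × 6 weeks = 12 weeks.

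**1. Fallback set beside the targets**

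| | Aim 3 | Aim 4 |
|---|---|---|
| Targets (months) | 6, 12, 24 | 12, 24, 36, 48 |
| Months named in the fallback | 6, 12, 24 | 6, 12 |
| Upper limit | 6 weeks (obscurely worded) | none |

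The Aim 4 fallback names one month that is not a target and omits three that are.

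*Literal reading.* Months early = target − anchor:

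| Target | Anchor month 6 | Anchor month 12 |
|---|---|---|
| 12 | 6 | 0 |
| 24 | 18 | 12 |
| 36 | 30 | 24 |
| 48 | 42 | 36 |

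These are the largest gaps, for a VL taken just after the anchor. The same early VL could fill several targets.

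*First VL after each target (as in Aim 3).* The direction is sensible, but nothing stops the value from falling in or beyond the next window.

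*Six or twelve months beyond each target.* Adding 12 months lands on the next target date; adding 6 does not. Neither is bounded.

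*How often the fallback is used.* The testing interval is not in the documents, so it is assumed. With regular testing at random phase, P(no VL in 84 days) = 1 − 84/(months × 30.4375):
- 3-monthly: 1 − 84/91.3 = 8%
- 4-monthly: 1 − 84/121.8 = 31%
- 6-monthly: 1 − 84/182.6 = 54%

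This is how often the fallback decides the value, not how often the value is wrong.

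**2. Meaning of success**

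No definition of success is given beyond the reference to failure. If success is the complement of CVF, a VL of at least 200 copies/mL that is not confirmed and not followed by discontinuation within 4 months counts as success, whatever its level. The second CVF arm is also unclear here: CAB+RPV LA has already stopped, and the text does not say whether stopping the *next* regimen is meant.

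**3. Model threshold**

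A logistic model is limited by the rarer outcome. No success rate for the next regimen is given. I take the 1–20% range of Table 4 (8.4), which concerns CAB+RPV LA, as an assumed failure risk p. When the 31st success is reached:
- expected number evaluable = 31/(1 − p)
- expected failures = 31p/(1 − p)
- P(no failures) = (1 − p)^31
- number needed to expect 31 failures = 31/p

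| p | N at 31 successes | Expected failures | P(no failures) | N for 31 failures |
|---|---|---|---|---|
| 1% | 31.3 | 0.31 | 0.73 | 3100 |
| 2% | 31.6 | 0.63 | 0.54 | 1550 |
| 3% | 32.0 | 0.96 | 0.39 | 1034 |
| 5% | 32.6 | 1.63 | 0.20 | 620 |
| 10% | 34.4 | 3.44 | 0.04 | 310 |
| 20% | 38.8 | 7.75 | 0.001 | 155 |

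The two ways of counting agree only at p = 50% (31/0.5 = 62).

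**4. Follow-up**

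More than 12 months is required for all four time points. Someone followed for 13 months meets the criterion for the 48-month model, although the outcome at month 48 cannot have been seen. Aim 3 matches follow-up to each time point.

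**The case against.** **The fallback is probably a drafting slip.** It resembles the Aim 3 sentence, where the sense is the first VL after the target. On that reading drift is modest under regular testing: at 6-monthly testing with no VL within 42 days of the target, the next comes at most 183 − 42 = 141 days (4.6 months) later, well before the next target. This stands. A reader might infer that late time points *will* be filled with values three years too old; that follows only from the literal reading. What remains is that the text does not say which reading holds, and that no reading sets a limit. Routine care need not follow a regular schedule, as the section itself says.

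**A single high VL is not stated to be a success.** A reader might infer that it is, and that success is therefore overstated. The protocol never says that success is the complement of CVF, and 8.3.2 also lists the below-50 and below-200 measures. Requiring confirmation is a deliberate choice shared with Aim 3. The second of two consecutive VLs need not lie in the window either, since sites send all measurements since the last data capture (8.5.2). All of this stands. The supportable point is that success is undefined, not that it is inflated by a known amount.

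**The threshold may be only a minimum.** The proviso about numbers comes first, and people who stopped because of failure or resistance may do worse on the next regimen than Table 4 suggests. Both are fair. But the proviso sets no number, and even at 20% risk the threshold is met with about 8 expected failures.

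**The aim is descriptive.** Annex 2 states that no hypotheses are tested. This lowers the severity but does not make the rules usable.

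**Conclusion.** The point holds and is of moderate severity.

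- **From the text alone:** the fallback is not tied to the 24-, 36- and 48-month targets, names a month outside Aim 4 and has no limit; success has no definition of its own; the model threshold counts successes where Aim 3 and the off-label analysis count failures; and follow-up is not matched to the time point.
- **Conditional on a reading:** the 36- to 42-month error at month 48 needs the literal reading. Classing an unconfirmed VL of at least 200 copies/mL as success needs success to be the complement of CVF.
- **Conditional on an assumption:** the 0.3 to 8 expected failures at 31 successes rest on a 1–20% failure risk borrowed from Table 4. That success is the commoner outcome is likely, but the documents do not state it.

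A later analysis plan could clarify the fallback and success, but to repair the threshold and follow-up rules it would have to depart from the protocol's wording. The documents do not support a claim that the reported success proportion will be too high by any given amount.

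**What to change.** In 8.6, AIM 4:

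1. **Fallback.** For each of months 12, 24, 36 and 48, if no VL lies within ±6 weeks, take the first VL after that target up to a stated limit. The limit must fall before the next window opens, at 12 months less 6 weeks after the target (365 − 42 = 323 days). Use no VL for more than one time point. Report the rest as missing, with counts. Copying the Aim 3 limit ("and at most 6 weeks after the measurement") would not do: six weeks counted from the target is already the edge of the window. A symmetric ±6-month window would not do either: a month-6 VL could stand for month 12, and adjacent windows would meet at months 18, 30 and 42.
2. **Success.** State whether success is the complement of CVF, and which regimen's discontinuation counts after CAB+RPV LA has stopped. Report the below-50 and below-200 copies/mL measures from 8.3.2 at these time points alongside the CVF-based outcome.
3. **Model.** Fit it only when the smaller of successes and non-successes exceeds 30, with follow-up matched to each time point.

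The change is a few sentences and needs no new data. The cost is more results shown as missing and fewer models fitted. For illustration, Table 4's largest scenario, 1000 initiators with 20% discontinuing, gives 200 persons; 31 failures among them would need a risk of 31/200 = 15.5%. The model may therefore seldom run, which is an accurate reflection of the information available.
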